- a Patients who do not meet the criteria for participation in this trial (screen failure) may be rescreened once. Patients must re-sign the ICF prior to re-screening, if the screening period exceeds 21 d. For both screening and re-screening, results of radiology scans performed prior to obtaining informed consent and within 28 d prior to randomization may be used. However, in case of signs of rapid progression, a new tumor evaluation may be necessary to obtain a reliable baseline assessment.
- b Patients who discontinue trial treatment for whatever reason, will return to the clinic for EoT visit within 21 d after last dose. The visit at which response assessment shows (confirmed) progressive disease may be used as the EoT visit. The EoT visit and post-treatment follow-up period will only be performed after discontinuation of both trial drugs. The EoT visit and post-treatment follow-up period for patients in Arms 2 and 3 who will continue to receive add-on therapy will be performed as outlined in SOA2 (Section 1.3.2).
- c All AEs will be reported until 90 d after the last dose of trial treatment or until a new anti-cancer therapy is started. Additionally, in case a new anti-cancer therapy is started within 90 d after last treatment, the safety follow-up visit should be performed just prior to starting the new anti-cancer therapy. Adverse events after start of new anti-cancer therapy do not need to be reported unless a causal relationship to BNT111-01 or cemiplimab is suspected.
- d Patients who discontinue trial therapy prior to disease progression should continue to have regular efficacy assessments as scheduled per protocol, until disease progression, the start of next-line anti-cancer therapy, withdrawal of consent, or death, whichever occur first.

^{*} Visits C1D8, C1D15, C2D8, and C2D15 are not to be conducted in patients in Arm 3 (cemiplimab only).

Clinical Trial Protocol BNT111-01

Page 18 of 133 Version: 7.0 Date: 09 FEB 2023

- After the last trial visit, information on survival status and new anti-cancer therapy will be collected via phone calls, patient medical records, and/or clinic visits approximately every 3 mon until death (unless the patient withdraws consent for survival follow-up or the sponsor terminates the trial). If a patient asks to be withdrawn from survival follow-up, this request must be documented in the source documents and signed by the investigator.

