 - Else if the month is greater than the treatment start date month, the start date is assumed to be the month start point (01MONYYYY).

If complete end date is available and the start date assumed from the steps above is greater than the end date, then the assumed start date should be set to the end date.

Partial anti-cancer therapy start dates will be handled as follows:

Statistical Analysis Plan (SAP) BNT111-01

Page 33 of 78 Version: Final v7.0 Date: 05Mar2024

- If the start of subsequent anti-cancer therapy date is missing, this will be imputed to the date of the EOT visit.
- Missing day, month/year present: If the month/year is the same as the month/year of EOT Visit date, then impute missing start dates with EOT Visit date. Otherwise, for dates corresponding to a start date, impute with the first day of the month.
- Missing month/day, year present: If the year is the same as the year of EOT Visit date, then impute missing start dates with EOT Visit date. Otherwise, for dates corresponding to a start date, impute with the first day of the year.
- If the EOT Visit date is missing, the date of last treatment will be used for imputation.

Partial date of progression for prior cancer therapies will be handled as follows, for the derivation of the time since the first diagnosis subgroup:

- Assign the day to the 15th of the month.
- If the month/year is missing, the date of progression will not be imputed.

Partial diagnosis dates will be handled as follows, for the derivation of the time since the first diagnosis subgroup:

- Assign the day to the 15th of the month.
- If the month is missing, the initial diagnosis date is assumed to be mid-year point (01JULYYYY).
- Else if the month is not missing, the initial diagnosis date is assumed to be mid-month point (15MONYYYY).

For analysis of pharmacodynamic data:

- The actual date collected will be used. If the date is not available, the value will be considered as missing.
- The actual time of sample collection will be used. If the time is not available, the value will, at the discretion of study pharmacodynamics analysist (in consultation with BioNTech), be considered as missing or imputed to be the nominal sampling time.

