8.4 Efficacy analyses

8.4.1 Primary analysis

The primary analyses will be performed using the CCI set.

Definition of primary endpoint

Overall Response Rate (ORR) defined as the proportion of patients in whom a CR or PR is observed as best overall response by blinded independent central review (BICR).

The BICR will provide a response for each patient assessment using the RECIST[©] 1.1 guidelines.

Main analytical approach

The primary statistical objective is to demonstrate that the ORR of BNT111+cemiplimab is greater than CCI using an overall significance level of CCI using an overall significance level of

[figure not shown]
The following null and alternative hypothesis are defined:

[figure not shown]
Statistical Analysis Plan (SAP) BNT111-01

Page 37 of 78 Version: Final v7.0 Date: 05Mar2024

The best overall response for a patient is defined as the best response across all responses prior to the start of new anti-cancer therapy for that patient. It is noted that a tumor response of SD can be confirmed from 36 days after first dose of study drug as the tumor assessment at week 6 (day 42) can be performed in a +/- 1 week window.

[figure not shown]
Statistical analysis

Additionally, a swimmer plot for duration on treatment and overall response assessments based on RECIST for BICR assessment will be presented based on set, add-on treatment set and combination of both (show both periods, including only for patients entering add-on treatment set). For IA1 the plot was generated for patients with BOR of CR/PR/SD and for IA2 the plot will be generated for patients with BOR of CR/PR/SD/PD/NE (for BICR data, the category Non-CR/Non-PD will be added). Tumor response and overall response will be listed.

Sensitivity analysis

Additionally, sensitivity analysis based on confirmed CR/PR (RECIST 1.1) for BICR assessment for the CCI set will be performed.

Page 38 of 78 Version: Final v7.0 Date: 05Mar2024

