10.5 Appendix 5: Censoring rules

Table 5.1 Censoring Rules for PFS, DOR & DDC Based on Food & Drug Administration (FDA) Guidelines

For calculation of 2 or more missed consecutive scheduled assessments, see the text after the censoring rules tables.

If a subject met multiple censoring criteria, the earliest censoring date will be used.

Situation (Censoring Order)	Date Patient Has Event or is Censored	Situation Outcome
Inadequate baseline assessment* (1)	Randomization date	Censored
Inadequate post-baseline assessments* (2)	Randomization date	Censored
* Not applicable to DOR and DCR		
Progression documented on or between scheduled tumor assessments	Date of first objective tumor assessment showing objective progression	Progressed (Event)
Progression documented not after 2 or more missed consecutive scheduled assessments during the treatment period or not after 1 or more missed scheduled assessments during the Follow-up period	For RECIST 1.1, the Date of objective progression / for iRECIST, the date of iUPD if progression associated with that iUPD has been confirmed.	Progressed (Event)
Death (and progression has not occurred previously) not after 2 or more missed consecutive scheduled assessments during the treatment period or not after 1 or more missed scheduled assessments during the Follow-up period	Date of death	Death (Event)

Statistical Analysis Plan (SAP) BNT111-01

Page 71 of 78 Version: Final v7.0 Date: 05Mar2024

Situation (Censoring Order)	Date Patient Has Event or is Censored	Situation Outcome
Death without objective progression	Date of death	Death (Event)
Death or progression after 2 or more consecutive missing scheduled assessments during the treatment period or after 1 or more missed scheduled assessments during the Follow-up period (3)	Date of last adequate assessment with evidence of no progression; if no adequate assessment exists then censored at the randomization date.	Censored
New anti-cancer therapy started prior to progression or death (4)	Date of last adequate assessment with evidence of no progression before anti-cancer therapy; if no adequate assessment exists then censored at the randomization date	Censored
No progression or death (6)	Date of last adequate assessment with evidence of no progression; if no adequate assessment exists then censored at the randomization date	Censored

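### Imputed next-line therapy dates ignore recorded scans, so a documented progression in follow-up can become an earlier censoring in PFS, DOR and DDC

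*SAP*

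**What the plan says.** SAP 8.1 (handling of missing data) sets the start of subsequent anti-cancer therapy as follows.

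- Date fully missing: "If the start of subsequent anti-cancer therapy date is missing, this will be imputed to the date of the EOT visit".
- Day missing: the EoT date if month and year match those of EoT. "Otherwise, for dates corresponding to a start date, impute with the first day of the month".
- Day and month missing, same year as EoT: "If the year is the same as the year of EOT Visit date, then impute missing start dates with EOT Visit date".
- Day and month missing, any different year: "Otherwise, for dates corresponding to a start date, impute with the first day of the year".
- Fallback when no EoT visit is recorded: "If the EOT Visit date is missing, the date of last treatment will be used for imputation".

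The imputed date is then used as a cut-off. In SAP 8.4.1, best overall response counts only responses "prior to the start of new anti-cancer therapy for that patient". In SAP 10.5, Table 5.1 order 4, a patient who starts new therapy before progression or death is censored for PFS, DOR and DDC at the last adequate progression-free assessment before that therapy. SAP 8.4.3.4 applies a similar cut to depth of response.

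On the data side, Protocol 1.3.1 (footnote d) says that patients who stop trial therapy before progression "should continue to have regular efficacy assessments as scheduled per protocol, until disease progression, the start of next-line anti-cancer therapy". Scanning also ends if the patient dies or withdraws consent.

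**The concern.** Under the protocol, next-line therapy ends tumor assessment. A protocol scan recorded after EoT is therefore itself evidence that next-line therapy had not begun by that day. The imputation makes no use of this evidence and can place the switch before a scan that shows it had not happened.

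The patients exposed are those who stop without PD and are followed by imaging. If one of them progresses on a follow-up scan, then starts a new treatment, and the start date is incomplete, the observed PD can be reclassified as post-switch data. PFS, DOR or DDC is then censored at an earlier scan. That removes a real event, and the censoring is informative because it occurs in patients known to have progressed. It tends to make durability look better than it was.

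**Working it through.** The plan attaches no figure to this rule, so there is none to reproduce. The check traces the rule through one case and then sizes it.

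**1. One patient, several recordings of the same switch.** Assume randomization and first dose on 3 January 2022. Scans follow the schedule: week 6 on 14 February, week 12 on 28 March (no PD) and week 21 on 30 May (PD). EoT is 15 April, on the investigator's decision and without PD. Next-line therapy truly starts in June 2022. SAP 8.1 gives 1 month = 30.4375 days.

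| Start recorded as | Imputed start | PFS under order 4 |
|---|---|---|
| June 2022 | 1 June | Event 30 May: 148 days, 148/30.4375 = 4.86 months |
| 2022 | 15 April (EoT) | Censored 28 March: 85 days, 2.79 months |
| Missing | 15 April (EoT) | Censored 28 March: 85 days, 2.79 months |
| Missing, EoT also missing, last dose 25 March | 25 March | Censored 14 February: 43 days, 1.41 months |

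The last row uses the 21-day limit between last dose and EoT in Protocol 7.1 (15 April − 21 days = 25 March). Only the first row gives the result that the scans support.

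**2. Change the reason for stopping to related toxicity.** Table 5.1 order 7 now also applies. It makes a progression documented in follow-up an event on its own date, 30 May. Order 4 still censors on 28 March. The table's tie-break, earliest date, is worded for patients who meet several censoring criteria, and order 7 is an event row. Order 4 has the lower number. The text does not decide between them.

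**3. How often a partial date crosses a real PD.** Take a follow-up PD, with therapy starting g days later in a month or year other than that of EoT, and PD dates spread evenly. The first-of-month date precedes the PD when both fall in the same month and the PD is not on the 1st: share = (30.4 − g − 1)/30.4. For 1 January: (365 − g − 1)/365.

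| g (days) | First of month | 1 January |
|---|---|---|
| 7 | 22.4/30.4 = 74% | 357/365 = 98% |
| 14 | 15.4/30.4 = 51% | 350/365 = 96% |
| 21 | 8.4/30.4 = 28% | 343/365 = 94% |
| 28 | 1.4/30.4 = 5% | 336/365 = 92% |

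The gaps g are assumptions.

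**4. Scheduled scans between imputed and true start.** Averaged over EoT on days 22 to 730, with the protocol's scan target days: a 30-day gap holds 0.42 scans (0 to 1), 90 days 1.23 (1 to 2), 180 days 2.39 (2 to 4) and 364 days 4.61 (4 to 6). First-of-month imputation shifts the date by at most 30 days. A missing month can shift it by up to about a year. A fully missing date has no upper bound.

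**5. Patients with such dates.** Assume 10–20% of the 90 Arm 1 patients stop without PD and 5–15% of those have an incomplete next-line date: 90 × 0.10 × 0.05 = 0.45, and 90 × 0.20 × 0.15 = 2.7. This counts incomplete dates. Multiplying by the first-of-month shares in step 3 gives 0.45 × 0.05 = 0.02 to 2.7 × 0.74 = 2.0, and that still supposes that every one of them had a follow-up PD.

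**6. ORR.** A response before the imputed date is kept. Only a first response inside the gap is lost. If all 90 Arm 1 patients form the denominator, each such loss lowers ORR by 1/90 = 1.11 points.

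**The case against.** The best defense is that early imputation is a deliberate safeguard: it avoids crediting trial treatment with responses to the next line. For ORR this stands. A loss there works against the claim that ORR exceeds its threshold, and moving the date behind every scan could credit a next-line response to trial treatment. It does not carry over to PFS and DOR, where the same convention deletes progressions.

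Incomplete dates may also be rare. Subsequent therapy is collected at EoT, both safety visits, efficacy follow-up and survival follow-up. A safety visit is due just before any new therapy begun within 90 days of last treatment, and discrepant data are queried. PFS and DOR carry no formal group comparison, and OS is untouched. All of this limits the size and stands.

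Three stronger readings are tempting but unsupported.

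- *A follow-up PD after a toxicity stop is certainly lost.* Order 7 points the other way. The finding is an unresolved conflict.
- *The last-dose fallback routinely erases the PD that ended treatment.* Protocol 6.3 allows treatment through initial radiological progression, confirmation comes 4 to 12 weeks later, and PFS uses the first PD. That PD may well precede the last dose. The fallback also needs both dates to be incomplete. A PD on the EoT date itself is not after the imputed start and appears to be kept for PFS.
- *About 0.5–3 patients have their result changed.* That range counts incomplete dates. Changed outcomes are fewer.

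**Conclusion.** The point holds in a limited form. The imputation can contradict recorded scans, and through order 4 it can turn a documented PD into an earlier censoring for PFS, DOR and DDC in patients who stop without progression. After a related-toxicity or 'other' stop, orders 4 and 7 give opposite outcomes and the SAP does not choose. The effect on ORR is confined to a first response after stopping and inside the gap, and it is conservative.

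The size cannot be fixed from the documents, which give no rate of incomplete dates. Under the assumed inputs, at most about 0.5–3 Arm 1 patients have such a date. This would not overturn the trial's conclusion on ORR. It matters most for DOR, which rests on responders alone. The reasoning assumes that protocol scanning stops at next-line therapy, as the protocol requires.

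**What to change.** In SAP 8.1, for PFS, DOR and DDC, impute the start as the latest of:

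- the EoT date (last dose if EoT is missing);
- the day after first documented PD;
- the first day of the known month or year.

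Cap it at the end of the known period, death or last contact. State that a PD documented before any known switch date is an event. In Table 5.1, say which of orders 4 and 7 takes precedence.

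For BOR and ORR, keep the current rule as primary. Add a sensitivity analysis that floors the imputed date at the day after the last protocol assessment. List all imputed dates beside the scan dates, so that any scan done after a true switch can be seen.

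The cost is a few sentences, one derivation and one listing, with no new data. A few patients may move from censored to event, so PFS or DOR may look slightly less favorable. Flooring also assumes that no scan was done after an undocumented switch, which is why it should remain a sensitivity analysis for ORR.

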8.2 Patient disposition

For the screened set, the number and percentage of patients having failed screening will be presented along with a summary of the primary reason for screening failure. A summary of reason for violation of inclusion/exclusion criteria will also be presented.

Statistical Analysis Plan (SAP) BNT111-01

Page 34 of 78 Version: Final v7.0 Date: 05Mar2024

The number and percentage of patients in each analysis set will be summarized by treatment group and overall for randomized patients. For each analysis set (Section 7.1) the number and percentage of patients being excluded from the analysis set will be presented by treatment group and overall along with a summary of the reasons for exclusion based on the ITT set.

For the ITT set the number and percentage of patients who were randomized and treated will be presented. Also, the number of patients on treatment and who are off-treatment will be summarized. Patients who are "off-treatment" will be the patients who received at least one dose of trial treatment and then discontinued from trial treatment. Also, for the ITT set the number and percentage of patients having discontinued from trial treatment will be presented by treatment group and total along with a summary of the primary reason for premature treatment discontinuation (e.g., adverse events, investigator's decision, disease progression, death, withdrawal of consent, lost to follow-up). The percentages for on/off-treatment and treatment discontinuation will be based on treated patients. The summary will also be repeated for Add-on treatment set and mITT set.

For the ITT set, the number and percentage of randomized / treated patients will be presented by country and site including the number and percentage of IPDs (by type, subtype (as appropriate), treatment group and total).

The number of patients who entered the efficacy follow-up (on trial/off-trial – for IDMC TFLs) and the number of patients who discontinued from the trial together with the reasons for discontinuation will be summarized for the patients in ITT by treatment and total. For trial discontinuation, efficacy follow-up, survival follow-up the percentages will be based on randomized patients.

The patients who entered efficacy follow-up will be selected based on the below definition.

"Patients where EOT had occurred and reason for EOT is NOT progression and new cancer treatment has not started and EOS has not yet occurred."

The summary of efficacy follow-up will be provided for Add-on Treatment set and mITT set as well.

In addition, survival follow-up status including entered (on/off survival follow-up) reason for discontinuation from survival follow-up and total number of deaths will be summarized by treatment group and total for the ITT set, Add-on Treatment set and mITT set.

The number of patients randomized by treatment group and randomization strata (from IWRS) will be presented based on ITT set.

8.3 Baseline characteristics

8.3.1 Demographics

Demographic and baseline variables will be summarized for patients in the ITT set. Age (years), weight (kg), height (cm), will be summarized as continuous data. Age (<70 years vs ≥70 years), Gender (male vs female) and race (Black or African American, American Indian or Alaska Native, Asian, Native Hawaiian or Other Pacific Islander, White and Not Reported)

Statistical Analysis Plan (SAP) BNT111-01 Page 35 of 78 Version: Final v7.0 Date: 05Mar2024

and Ethnicity (Hispanic or Latino, Not Hispanic or Latino and Not Reported) will be summarized as categorical data.

Demographic and baseline variables will be summarized for the patients in Add-on treatment set and mITT set as well.

A patient data listing will be provided.

8.3.2 Disease characteristics

The following disease characteristics will be summarized for patients in the ITT set.

- · Histologic subtype (cancer subcategory),
- BRAF V600 Mutation status,
- Tumor stage at diagnosis (American Joint Committee on Cancer Staging (AJCC)),
- Tumor stage at trial entry (baseline)
- · Location at the initial diagnosis

The summary will be repeated for Add-on Treatment set and mITT as well.

A patient data listing will be provided.

8.3.3 Prior cancer therapies

Prior anti-cancer treatments (as collected on the CRF) will be summarized for the ITT set, Add-on Treatment set and mITT set.

Any prior surgery (curative, palliative and diagnostic), any prior radiotherapy (Adjuvant, Neoadjuvant, Metastatic, Maintenance and unknown), intent, number of therapy lines, prior cancer therapy types, number of prior anti-PD-1/anti-PD-L1 therapies (1 vs >1), duration of anti-PD-1/anti-PD-L1 therapy prior to disease progression (≤6 months, 6-12 months, ≥12 months) and time from anti-PD-1/anti-PD-L1 discontinuation to progression (on therapy, >1 month and ≤6 months, >6 months) will all be summarized as categorical data.

A listing of prior anti-cancer therapies will be provided.

8.3.4 Prior and concomitant medication/procedures/non-drug therapy

Prior and concomitant medications will be summarized for the ITT set and the Add-on Treatment set.

Prior and concomitant medications/non-drug therapies will be defined using start and stop dates recorded, relative to the first and last dose of trial medication (BNT111 or cemiplimab).

A prior medication/prior non-drug therapy will be defined as any medication/ non-drug therapy taken 28 days prior up to (but not including) the start date of trial treatment.

A concomitant medication/concomitant non-drug therapy will be defined as any medication/non-drug therapy either ongoing at the start of trial medication or with a start date on or after the first dose of trial medication up to the SFU2 visit. Section 8.1 contains details of how partial and missing dates will be handled.

Statistical Analysis Plan (SAP) BNT111-01

Page 36 of 78 Version: Final v7.0 Date: 05Mar2024

Medications will be coded using the World Health Organization Drug Dictionary (WHODrug) version B3 March 2020. Resulting in Anatomical-Therapeutic-Chemical (ATC) codes indicating therapeutic classification.

The number and percentage of patients taking prior and concomitant medications will be summarized by ATC therapeutic class (ATC level 2), ATC pharmacological class (ATC level 3), and chemical substance (ATC level 5) for each treatment group and total. The summary will be presented alphabetically.

Procedures and Non-drug therapies will be coded using the Medical Dictionary for Regulatory Activities (MedDRA®) version 23.1 or later version if used.

Procedure and non-drug therapies will be listed only.

Patient data listings will be provided.

